1.1.3 Estimand

The estimand of the primary objective is defined by the following 5 attributes:

- Treatment: Single dose of AT132
- Population: Male participants with ventilator-dependent XLMTM, as defined by the inclusion/exclusion criteria of the study
- Endpoint: Change from baseline in hours per day of ventilation support at Week 24
- Intercurrent events and their corresponding strategies: For study discontinuation due to death or due to lack of efficacy, a composite strategy will be adopted, where participants with the intercurrent event before Week 24 having missing observation(s) after the intercurrent event will have those missing observations(s) imputed by unfavorable values ([Appendix 2](#))
- Population level summary: Mean change from baseline, by AT132 dose level

The estimand framework described above will be applied to all relevant primary and secondary efficacy endpoints.

1.2 Study Design

This is a Phase 1/2/3, randomized, open-label, ascending-dose, delayed-treatment concurrent control clinical study to evaluate the safety and efficacy of AAV8-delivered gene therapy in XLMTM participants aged less than 5 years old. Participants will receive a single dose of AT132 and be followed for safety and efficacy for 10 years.

The study consists of 2 parts. Part 1 would establish the optimal dose of AT132. Part 2 would confirm the safety and efficacy of AT132 at the optimal dose level. The following describes how each part was designed and the changes as of protocol v8.

Part 1 (fully dosed as of protocol v8):

A maximum of 3 dose levels of AT132 are planned for evaluation in Part 1 of this study (Figure 1). Four participants will be enrolled in each dose level cohort, including 1 participant in each dose level cohort randomized to control with delayed administration of treatment. The first participant in each dose level cohort will be assigned to receive AT132 and will be treated as a sentinel participant. Subsequent participants in that dose level cohort will be randomized (2:1) to treatment or control with delayed treatment if there are no safety concerns after at least 4 weeks of post-dose data from the sentinel participant is evaluated by the chair of the data monitoring committee (DMC). Dose escalation to the next dose level will be considered after evaluation of at least 4 weeks of data from all participants dosed at the current dose level. Following the dose escalation portion of the study, an optimal dose will be determined in conjunction with the DMC, and control participants will be treated at the optimal dose level.

This study's independent DMC will monitor participant safety and provide recommendations to the Sponsor regarding dose level determination, cohort expansion, and safety and study conduct matters.

Control participants will generally have the same assessments as treated participants but on a less frequent schedule to lessen the burden of study participation. It is anticipated that control participants will participate for at least 24 weeks before an optimal dose is determined and the participant can be administered AT132. Following determination of the optimal dose, control participants will undergo pretreatment baseline procedures to confirm that they remain eligible to receive treatment with AT132 at the optimal dose. Once eligible, control participants will be dosed with AT132, and will initiate the post dose procedures.

Treated participants will be administered a course of concomitant prophylactic glucocorticoid (oral prednisolone) therapy commencing 1 day prior to AT132 dosing, and continuing for a period of approximately 8 weeks, then tapering from the original dose over an additional 8 weeks, per Investigator discretion, as a preventative measure for immune-mediated hepatic injury, which has been observed in gene therapy clinical studies with AAV. Tapering duration may be altered and/or supplemental administration of IV steroids (e.g., methylprednisolone) or other immunosuppressive regimens may be considered in cases of potential malabsorption of oral medications.

Participants will be followed for a total of 10 years following AT132 administration. See Figure 1 for the individual study participation timeline (Parts 1 & 2) through Week 48.

Part 2 (described herein as planned prior to protocol v8; partially dosed as of protocol v8):

In Part 2, the optimal dose of AT132 will be evaluated in an expansion cohort of 10 participants age matched randomized to a study drug or a delayed-treatment control group

(1:1 allocation ratio). A pair of participants in each group will be prospectively best-matched based on age (± 6 months) before being randomized to 1 of the treatment arms (AT132 vs. delayed-treatment control). The administration of study drug and concomitant prophylactic glucocorticoids, and the assessment of safety will be the same as described in Part 1. Following collection of their Week 24 data, control participants will be administered AT132 and followed according to the Schedule of Events.

Part 2 as of protocol v8 and v9:

Following the review of benefit/risk profiles of the 1.0×10^{14} vg/kg and 3.0×10^{14} vg/kg dose levels, the Sponsor, in consultation with the DMC, determined that participants not yet dosed were to be administered the lower dose level (ie, the therapeutic dose), which is 1.3×10^{14} vg/kg as determined by the 2nd generation vg titer assay. Dosing of the 3 enrolled delayed-treatment controls who have not yet been dosed will not be conducted as described above for Part 2, but will resume at 1.3×10^{14} vg/kg as long as each participant meets a subset of inclusion and exclusion criteria prior to dosing. If any of these control participants is not eligible to be dosed, another eligible participant can be enrolled. Any new participant will not be considered a delayed-treatment control and therefore will not be required to wait 24 weeks before administration of study drug. Any new participant will be enrolled under all of the inclusion/exclusion criteria (including Exclusion Criteria 12-14 required for Part 2 participants).

In addition to prophylactic glucocorticoids, participants will receive daily prophylactic ursodiol (ursodeoxycholic acid) beginning between Study Days -6 and -4. Participants will be followed according to the Schedule of Events.

As of protocol v10 and beyond:

This study does not allow for enrollment or dosing of any future participants.

See [Figure 2](#) for Overall Study Design.

Details of the schedule of clinical assessments are available in the protocol.

Figure 1 Summary of Individual Study Participation Timeline (Parts 1 & 2)

[figure not shown]
[figure not shown]

Figure 2 Overall Study Design

Notes: Delayed-treatment control subjects to be treated with AT132 after Week 24. As reflected in protocol v5, the Data Monitoring Committee (DMC) and Sponsor determined the therapeutic dose to be 3.0×10^{14} vg/kg and thus, dose escalation to the third originally planned 5.0×10^{14} vg/kg dose level (Cohort 3) did not occur.

a. An additional 3 subjects treated with 1.0×10^{14} vg/kg AT132 in Cohort 1 based on DMC recommendation.

b. Delayed-treatment control subjects from Part 1 treated with AT132 after the therapeutic dose was determined.

c. Additional subjects treated with 3.0×10^{14} vg/kg AT132 in Cohort 2 based on DMC recommendation.

d. No additional subjects will be dosed under this amendment.

e. Previously referred to as 1.0 and 3.0×10^{14} vg/kg. The 1.0×10^{14} vg/kg and 3.0×10^{14} vg/kg dose levels based on the 1st generation titer method equate to 1.3×10^{14} vg/kg and 3.0×10^{14} vg/kg, respectively, based on an analysis of all historical Study 002 drug product lots using the 2nd generation vg titer assay.

Source: Data on file.

Two database locks are planned for this clinical study. The first database lock is intended for will occur after all ongoing participants complete the Week 24 visit and prior to all participants completing the 10-year follow-up period or withdrawing. The second (final) database lock will occur after all participants have completed the study.

1.3 Randomization

Part 1: The first participant in each dose level cohort will be assigned to receive AT132 and will be treated as a sentinel participant. Subsequent participants in that dose level cohort will be randomized (2:1) to treatment or control with delayed treatment if there are no safety concerns after at least 4 weeks of post-dose data from the sentinel participant is evaluated by the chair of the DMC.

Part 2: (prior to protocol v8): Participants will be prospectively paired based on age (± 6 months) before being randomized to study drug or delayed-treatment control (1:1 allocation) to one of the treatment arms (AT132 vs. delayed-treatment control).

General: Randomization codes will be preassigned for each participant before enrollment into the cohort.

After confirmation of participant's eligibility by the Investigator, the Sponsor will provide to the Investigator the assigned dose or control designation for the participant number according to the randomization sequence and the order of participants eligible for randomization.

ASPIRO Part 2 participants that are ready to be randomized will fall into one of the following groups:

- If 2 age-matched participants are ready and eligible for randomization, then they will be randomized (with a separate request form for each participant)

- If only 1 participant is ready for randomization, then
 - Two more check-list-qualified age-matched participants will be identified and confirmed by study sponsor (using protocol check list) before any attempt for randomization
 - The request for randomization of the first participant will include the participant ID numbers for the additional 2 participants identified as confirmed potentials
 - Amongst the 2 participants competing for randomization into the second slot for the pair, the following hierarchy will be used to prevent any bias in selecting the second participant
 - Site readiness
 - Date enrollment/eligibility authorization received
 - Closest in age to the first participant already randomized in that pair group
 - Duration of participation in INCEPTUS
 - Tie-breaker #1: Regional Diversity (i.e., site with no participants has priority)
 - Tie-breaker #2: Country Diversity (i.e., country with no participant has priority)
 - The form for request for randomization of the second participant will need to have a complete list of the above bullets for prioritization in form of a table

Once 2 participants have been randomized into the same age-matched pair is complete.

This is an open-label study, and therefore there is no blinding of treatment assignment for the study.

The objectives of the study changed as a result of the study going on clinical hold. The intent changed to describe the safety and efficacy of participants being administered a low dose or a high dose of AT132. As such, data is not analyzed as randomized, but instead, data analysis is based on low dose or high dose received and excludes the two non-dosed delayed control participants.

2 STATISTICAL HYPOTHESES

Considering that the study is no longer able to address the stated objectives, there will be no statistical hypothesis testing. All summaries by treatment group will be descriptive in nature..

3 ANALYSIS SETS

In accordance with International Conference on Harmonization (ICH) recommendations in guidelines E3 and E9, the following analysis sets will be used for the analyses.

The determination of whether participants are included or excluded from the safety and efficacy analysis sets will be made prior to database lock.

The following analysis sets for participants treated with AT132 will be used:

- Full Analysis Set (FAS) is defined as all randomized and/or enrolled participants who received AT132 and had at least 1 postdose efficacy assessment. The participants will be analyzed based on the treatment actually received. The FAS will be used for summary of demographics and baseline characteristics, and analyses of all efficacy endpoints.
- Safety Analysis Set (SAF) is defined as all randomized and/or enrolled participants who received AT132. The participants will also be analyzed based on the actual treatment received as well as an “All dosed” group of all participants treated with AT132. The SAF will be used for summaries of demographics, baseline characteristics, participant disposition, and the analysis of the safety endpoints.

In each analysis set, 3 treatment groups are defined by: (i) Low Dose (AT132 1.3×10^{14} vg/kg), (ii) High Dose (AT132 3.5×10^{14} vg/kg), and (iii) AT132 Dosed Total (not applicable to efficacy endpoints).

Listings will include all randomized participants unless otherwise stated.

4 STATISTICAL ANALYSES

4.1 General Considerations

The study is no longer able to address the stated objectives, hence the statistical analysis will provide descriptive summaries by treatment groups.

Continuous data will be summarized descriptively including the number of participants (n), mean, standard deviation (SD), median, minimum and maximum. Categorical data will be summarized by frequencies and percentages. Percentages by categories will be based on the number of participants with no missing data, i.e. the percentages for the non-missing categories will add up to 100%.

All data summarization and analyses will be performed using SAS® Version 9.4 or higher on Red Hat Enterprise Linux. Specifications for table, figures, and data listing formats can be found in the TLF specifications.

4.2 Study Participants

Participant disposition will be summarized for all randomized participants. Demographics and baseline characteristics will be summarized for both the FAS and SAF populations.

4.2.1 Participant Disposition

Disposition of participants will be summarized by AT132 dose level and overall. Denominator for percentages is the number of participants treated, unless otherwise specified.

The participant disposition summary will include:

- Number of participants with signed informed consent
- Number and percent of participants who were randomized (denominator is the number of participants with informed consent)
- Number and percent of participants who were treated (denominator is the number of participants randomized)
- Number and percent of participants who were not treated (denominator is the number of participants randomized)
- Number and percent of participants who complete 24 weeks of follow-up after initial dosing visit
- Number and percent of participants who complete 48 weeks of follow-up after initial dosing visit
- Number and percent of participants who complete 5 years of follow-up after initial dosing visit
- Number and percent of participants who complete 10 years of follow-up after initial dosing visit.
- Number and percent of participants who complete the study
- Number and percent of participants in each analysis set (FAS and SAF)
- Number and percent of participants who prematurely discontinue from the study
- For discontinuation, the primary reason reported by the investigator will be summarized using count and percent of participants.

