4.2 Method of Assigning Subjects to Treatment Groups

Randomization codes will be preassigned for each subject before enrollment into the cohort. In Part 2, subjects will be matched with another subject close in age (± 6 months) and will then be randomized to study treatment or delayed-treatment control. Subjects enrolled under protocol v8 and beyond will be assigned to study treatment within Part 2.

After confirmation of subject's eligibility by the Investigator, the Sponsor will provide to the Investigator the assigned dose or control designation for the subject number according to the randomization sequence and the order of subjects eligible for randomization. For subjects not assigned to the delayed-treatment control arm, the Sponsor will coordinate shipment of the appropriate number of AT132 vials to the study site pharmacy. Further details regarding this process will be outlined in the Pharmacy Manual.

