7.3 Subject Disposition, Demographic Data, Baseline Characteristics, and Extent of Exposure

The number and percentage of study subjects who complete and discontinue the study as well as reasons for early discontinuation will be presented by low dose, high dose, and overall for the SAF.

Demographic and baseline measurements will be summarized by low dose, high dose, and overall on the FAS and SAF. Medical history will be summarized by low dose, high dose, and overall for the SAF.

Exposure will be confirmed based on the report of dosing recorded in the eCRF, and will be presented in a listing.

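### The disposition, deviation and registry-demographics tables are defined on randomized participants only, which read literally leaves out at least the two treated sentinel children

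*SAP*

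**What the plan says.** SAP 4.2 states: "Participant disposition will be summarized for all randomized participants". Within that table, SAP 4.2.1 sets a general rule, "Denominator for percentages is the number of participants treated, unless otherwise specified", and then departs from it for two rows: "Number and percent of participants who were treated (denominator is the number of participants randomized") and "Number and percent of participants who were not treated (denominator is the number of participants randomized"). SAP 4.2.2 summarizes major protocol deviations for participants who were randomized. SAP 4.2.4 adds a demographics table for all randomized participants; the SAP version history says it serves registry reporting. SAP 3 gives a default for listings: "Listings will include all randomized participants unless otherwise stated".

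On how children entered the study, SAP 1.3 says of Part 1: "The first participant in each dose level cohort will be assigned to receive AT132 and will be treated as a sentinel participant". Only subsequent children in the cohort are randomized, 2:1. Protocol 1.4.2 describes Cohort 1 in the same terms: one sentinel, then two children randomized to AT132 and one randomized to delayed treatment. For late enrollees, Protocol 4.2 says: "Subjects enrolled under protocol v8 and beyond will be assigned to study treatment within Part 2".

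The analysis sets in SAP 3 are wider. Both FAS and SAF take treated participants who were randomized or enrolled. SAP 3 also lists participant disposition among the summaries based on the SAF. Protocol 7.3 agrees: disposition "will be presented by low dose, high dose, and overall for the SAF".

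**The concern.** The FAS and SAF definitions make room for treated children who were never randomized. The participant-accounting outputs do not. A programmer who follows the text must either drop treated children from those tables or divide a count of treated children by a denominator that does not contain all of them.

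The study is now purely descriptive (SAP 2 and 4.1) and very small, so a complete account of every dosed child is a large part of what the report can offer. The deviation table is the most exposed output because no SAF version of it is planned. The all-randomized demographics table matters because it is meant for public reporting.

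Separately, the SAP names two different populations for the same disposition table.

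**Working it through.** **Which outputs use which population**

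| Output | Population in the SAP | Includes sentinels, read literally? |
|---|---|---|
| FAS, SAF (SAP 3) | randomized or enrolled, and treated | yes |
| Disposition (SAP 3) | SAF | yes |
| Disposition (SAP 4.2) | all randomized | no |
| Treated and not-treated rows (SAP 4.2.1) | denominator: number randomized | no |
| Follow-up and discontinuation rows (SAP 4.2.1) | denominator: number treated | yes, for the denominator |
| Deviations (SAP 4.2.2) | randomized | no |
| Extra demographics table (SAP 4.2.4) | all randomized | no |
| Listings, default (SAP 3) | all randomized, with exceptions allowed | no, unless another section overrides |

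**Head count.** No document states the final number enrolled or dosed, so it has to be built up.

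- Dosed by 08 July 2020 (Protocol 1.4.2): 6 low dose and 17 high dose.
- Delayed-treatment controls still undosed at protocol v8 (Protocol 3.1): 3.
- Total: 6 + 17 + 3 = 26. This matches the planned figure of about 16 + 10 = 26 (Protocol 3.3.3).
- Controls never dosed (SAP 1.3): 2. So 3 − 2 = 1 control was dosed later, at the low dose under the v9 rule.
- Low dose 6 + 1 = 7; high dose 17; dosed 7 + 17 = 24; never dosed 2.

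Cross-check on Part 1: Cohort 1 is 4 + 3 = 7. Cohort 2 is 4 plus an expansion that Protocol 1.4.2 gives as 3 to 5. With 5, Part 1 is 7 + 9 = 16, as planned. High dose is then 3 + 5 + 2 Part 1 controls + 5 Part 2 treated + 2 Part 2 controls = 17, as reported. With 3 or 4, Part 1 would be 14 or 15 and high dose 15 or 16.

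**Sentinels.** Two dose cohorts opened and the third did not, so two sentinels: one low dose, one high dose.

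**Effect if only the sentinels were not randomized.** Randomized = 26 − 2 = 24.

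- Treated 24/24 = 100%; not treated 2/24 = 8.3%; together 26/24 = 108.3%.
- Treated by dose received: low 7/(7 − 1) = 7/6 = 116.7%; high 17/(17 − 1) = 17/16 = 106.3%. This counts randomized controls under the dose they received and gives the two never-dosed controls no dose level.
- If the numerator is also limited to randomized children, treated is 22/24 = 91.7% and the rows sum to 100%, but 2 of the 24 treated children (8.3%) are missing.
- Deviation table: 1 of 7 low-dose children (14.3%) and 1 of 17 high-dose children (5.9%) are missing.

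**With all enrolled children as denominator:** treated 24/26 = 92.3%; not treated 2/26 = 7.7%; sum 100%.

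**The case against.** The best counter-argument is that the documents often use randomization for everyone who enters. SAP 1.3 and Protocol 4.2 preassign codes for every participant. Protocol 5.3 says that eligible subjects are randomized, without excepting sentinels, and the screening schedule marks randomization for all. If the database flags every entrant as randomized, no child is lost and the percentages behave. This lowers the practical risk. It does not settle the text: the SAP never defines the term so broadly, and SAP 1.3 and Protocol 1.4.2 separate sentinels from randomized children. Nor does it remove the conflict between SAP 3 and SAP 4.2, because the two never-dosed controls belong to one disposition population and not the other.

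Two stronger readings are tempting, and the documents do not support them.

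- *Safety listings lose treated children.* The default listing rule allows exceptions, and the specific sections largely supply them. SAP 4.6 sets safety analysis on the SAF. SAP 4.6.1, 4.6.2.1 and 4.6.2.3 call for all adverse events of special interest, laboratory results and vital signs to be listed, and SAP 4.7.1.1 covers all available antibody titers.
- *Ten treated children are outside the denominator and the treated row reads 24/16 = 150%.* This needs the 3 + 5 expansion children also to be non-randomized. Protocol 1.4.2 calls them additional subjects and is silent on how they were allocated.

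Three further limits stand. Only two disposition rows use the randomized denominator. With sentinels alone, the overall treated row is exactly 100%; the excess appears only in the sum or by dose. The v8 assignment rule shows that the protocol distinguishes assigning from randomizing, but no child is shown to have entered under it. Protocol 7.3 adds little weight, because Protocol 7 lets the final SAP govern where the two differ; the conflict that matters is inside the SAP.

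**Conclusion.** The point holds as an inconsistency in populations and denominators. The text makes at least two treated children, the sentinels, non-randomized. Read literally, they fall out of the deviation table and the registry demographics table, and the treated and not-treated rows rest on a denominator that excludes them. Disposition is also assigned to two populations within the SAP.

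The 108.3% total and the 7/6 and 17/16 ratios assume 26 enrolled, 24 dosed, no replacement child enrolled, and one of the last three controls dosed at the low dose. These figures are derived, not stated. The textual point does not depend on them. More than two children are affected only if the expansion children were also not randomized, which the documents do not say. No FAS or SAF efficacy or safety result changes.

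**What to change.** - In SAP 4.2, 4.2.1, 4.2.2, the extra demographics table in 4.2.4 and the default listing sentence in SAP 3, replace randomized with enrolled (randomized or assigned).
- In SAP 4.2.1, use the number enrolled as the denominator for treated and not treated.
- Reconcile SAP 3 with SAP 4.2 on the disposition population. Enrolled participants is the natural choice, because the not-treated row has nothing to count on the SAF.
- Optionally, add a disposition row that separates assigned from randomized children, which would also record how the expansion children entered.

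The cost is wording in five places and, at most, a population flag in the programming. No analysis model, estimate or safety summary changes, and there is no evident downside.
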